1.2.4.3. Rationale for monitoring of hematology parameters

Emphasis on “minimal risk” is imperative for the protection of the pediatric population participating to research studies where blood sample volume limits is a critical parameter. To stay within blood sampling limits that are consistent with physiological “minimal risk” in this young and vulnerable population, but also to minimize any development of needle aversion, blood draws for the determination of hematological parameters are scheduled at Day 1 and Day 31 (corresponding to the first day after administration of the vaccine). Additional specimens will be drawn if any \geq Grade 1 for platelet decrease is detected at Day 1 or Day 31 to investigate clinical symptoms suggestive of low platelets. Blood samples collected within the screening window will serve as baseline for the immunological analysis and for the hematology and biochemistry check-up before vaccination. Consequently, the maximum blood draw volumes collected per protocol have been restricted to 9.0 mL within 24 hours and 26.2 mL over eight weeks (refer to [Table 5](#) and [Table 7](#)). For investigational sites without a laboratory in proximity capable to perform whole blood stimulation [WBS] necessary for the CMI assay the volumes will be less. Of note, it is considered that blood sample volumes ranging from 1 to 5% of total blood volume within 24 hours and up to 10% of total blood volume over 8 weeks are consistent with the limited evidence available on the minimal physiological risk for healthy children [[Howie](#); 2011]. The total blood volume of a child is around 75 to 80 mL/kg (85 to 105 mL/kg in the neonatal period). Considering a girl of 12 months of age with a low weight of 7.3 kg (5th percentile [[WHO](#); 2006]), the minimal individual total blood volume in the study population would be 547.5 mL and therefore the safer limits of blood draw volumes would range from 5.5 to 27.4 mL within 24 hours and be limited to 54.7 mL over 8 weeks. To minimize any development of needle aversion, pain relief by means of a topical local anesthetic may be offered to infants prior to any blood sampling requested by the protocol at the discretion of the investigator.

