If we assume platelet counts in healthy infants between 12 and 23 months follow a normal distribution with a mean of 300,000 platelets/mm³ and a standard deviation of 75,000 platelets/mm³, then we would expect 0.04% of unvaccinated infants to have a count below 50000 platelets/mm³, which is the cut-off for a Grade 3 thrombocytopenia. To rule out a four-fold or greater increase, we would need to show that the mean platelet count does not fall below 190,000 platelets/mm³ with a standard deviation of 47,500. The sample size needed to rule out a 110,000 platelets/mm³ decrease due to vaccination with 84% power when vaccination has no effect on platelet count is 16 infants per dose cohort (8 per group). Sample size is based on a one-sided 0.025 test of non-inferiority using the Mann-Whitney statistic (PASS 12, Non-inferiority Tests for Two Means using Differences).

The Bayesian approach to predict the probability of no Grade 3 or higher thrombocytopenia in the future 16 subjects per dose cohort will be conducted by treating the mean of platelet counts μ as a random variable with a normal prior distribution $N(\mu_0, \sigma_0^2)$, where μ_0 and σ_0 will be determined by using laboratory normal

range. For this analysis the range of 150,000 to 450,000 platelets/mm³ will be the focus. Based on this laboratory range, μ_0 would be 300,000, a mean of the range, and σ_0 would be 75000, an approximate of a standard deviation of data sampled from this normal range. After 16 infants complete the two-dose vaccination schedule, a posterior distribution of μ will be calculated based on the prior of μ and the observed platelet counts from Day 31. The posterior predictive probability of no Grade 3 or higher thrombocytopenia in the future 16 subjects per dose cohort will be calculated, and sensitivity on the prior will be assessed.

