After the first 16 infants of a dose cohort have completed the two-dose vaccination schedule, the 95% CI for the difference in mean platelets at Day 31 between vaccinees and placebo recipients will be calculated along with the posterior predictive probability of no Grade 3 or higher thrombocytopenia in the future 16 infants. If the lower boundary of the 95% CI is above 110,000 platelets/mm³ and the predictive probability is sufficiently high (e.g., 80% or more), the IDMC may recommend enrolling infants into the next dose cohort without completing enrolment in the current cohort. However, if a Grade 3 or higher thrombocytopenia occurs in a vaccinated infant at any time point or if there is a significant safety concern with another laboratory parameter such as hemoglobin or neutrophils, the IDMC may recommend continuing enrolment into the lower dose cohort. (Amended 10 December 2017)

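### The Day 31 platelet comparison behind early escalation ignores the Screening count; prespecified adjustment would narrow its interval if the two counts correlate above about 0.3

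*Protocol*

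**What the plan says.** Protocol section 11.4 bases part of the early-escalation decision on platelets once the first 16 infants of a step have had both doses: "the 95% CI for the difference in mean platelets at Day 31 between vaccinees and placebo recipients will be calculated". The condition reads "If the lower boundary of the 95% CI is above 110,000 platelets/mm³ and the predictive probability is sufficiently high". If it is met, the IDMC may recommend opening the next step without filling the current one.

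The sizing text in the same section aims to "rule out a 110,000 platelets/mm³ decrease due to vaccination with 84% power", "when vaccination has no effect on platelet count", with 8 infants per group and a "one-sided 0.025 test of non-inferiority using the Mann-Whitney statistic". Counts in unvaccinated infants are taken as normal with "a mean of 300,000 platelets/mm³ and a standard deviation of 75,000 platelets/mm³".

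Section 3 has hematology drawn from all infants at Screening and on Day 31. Section 1.2.4.3 gives the Screening sample its role: "Blood samples collected within the screening window will serve as baseline for the immunological analysis and for the hematology and biochemistry check-up before vaccination". Section 6.2.2.2.1 minimises on center only. The SAP tabulates platelets against Screening in Templates 24 and 25, but describes neither the escalation interval nor any adjusted platelet analysis.

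**The concern.** As written, the comparison is a plain difference of two Day 31 means with about 8 infants in each. Its width is set by the spread between infants, and some of that spread is already visible before vaccination. If an infant's Screening count predicts the Day 31 count, leaving it out discards usable information in a very small sample.

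A chance difference in starting counts also moves the estimate. Nothing in the allocation balances platelets, and the difference in baseline means has an SD of 75,000 × √(1/8 + 1/8) = 37,500. That imbalance carries into the Day 31 difference multiplied by the correlation.

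The comparison bears on thrombocytopenia, the protocol's named a priori safety concern. It feeds the decision to open a higher dose after 16 rather than 32 infants.

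**Working it through.** **Inputs from Protocol section 11.4.** 8 per group; SD 75,000; margin 110,000; true difference 0; one-sided 0.025, which is the lower end of a two-sided 95% CI.

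**Assumed.** ρ, the Screening-to-Day-31 correlation, is in neither document; 0 to 0.7 is shown. For the calculation, passing means a lower bound above −110,000 (vaccine minus placebo), in line with the sizing text; the printed condition carries no minus sign.

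**1. The plan's own figure.** SE = 75,000 × √(1/8 + 1/8) = 37,500, and 110,000 / 37,500 = 2.933. Normal approximation: Φ(2.933 − 1.960) = Φ(0.973) = 83.5%, which matches the stated 84%.

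**2. Small-sample version.** Non-central t with 14 df, non-centrality 2.933 and critical value 2.145 gives 77.9%. An exact Mann-Whitney test on normal data, simulated, gives about 75.5%. The mean half-width of the unadjusted t interval is 79,000.

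**3. ANCOVA on the Screening count.** Residual SD = 75,000 × √(1 − ρ²), with 13 df. SE² = s² × (1/8 + 1/8 + d²/Sxx), where d is the difference in baseline means and Sxx the pooled within-arm sum of squares of the baseline. On average the d²/Sxx term inflates the variance by 13/12.

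Example at ρ = 0.5: residual SD = 64,952; SE = 64,952 × √(0.25 × 13/12) = 33,802; non-centrality = 110,000 / 33,802 = 3.254; critical value 2.160; power 85.2%. Simulation with 200,000 trials per value gives the following.

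| ρ (assumed) | Power, ANCOVA | Mean half-width |
|---|---|---|
| 0 | 74.3% | 82,600 |
| 0.3 | 78.1% | 78,800 |
| 0.4 | 81.2% | 75,700 |
| 0.5 | 85.2% | 71,500 |
| 0.6 | 90.1% | 66,000 |
| 0.7 | 95.2% | 59,000 |

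The unadjusted interval stays at about 78% and 79,000 throughout. Break-even is at ρ of about 0.3, and 84% is reached at about 0.47.

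**4. Simple change from Screening.** This is not a substitute: 63.5% at ρ = 0.3 and 77.9% at ρ = 0.5, so it beats the unadjusted interval only above 0.5.

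**5. Chance imbalance of one SD (37,500), no vaccine effect.** The shift carried into Day 31 is ρ × 37,500, which is 11,250 at ρ = 0.3 and 18,750 at ρ = 0.5. At ρ = 0.5 the unadjusted criterion passes 63% of the time if vaccinees start lower and 92% if they start higher; ANCOVA passes 85% either way. At ρ = 0.3 the figures are 69% and 86%, against about 78% for ANCOVA.

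**6. True fall of 110,000.** Over all allocations, both methods pass about 2.5% of the time. If vaccinees happen to start one SD higher, at ρ = 0.5, the unadjusted rate is between 4% and 5%, while ANCOVA stays close to 2.5%.

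**The case against.** The unadjusted interval is valid. Averaged over randomisation it has its nominal error rate, and chance imbalance is already part of its width. The gain from adjustment depends on an unknown. On the nominal schedule Screening can precede Day 31 by up to 30 + 30 + 1 = 61 days. Infants with any Grade 2 or worse, or clinically significant Grade 1, screening abnormality are excluded. Both may lower the correlation. ANCOVA at 8 per arm costs a degree of freedom and assumes a linear relation with a common slope. All of this stands, and it is why the point is conditional.

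Three stronger readings are tempting and are not supported.

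- **Adjustment always narrows the interval.** It does not below a correlation of about 0.3.
- **An unlucky imbalance blocks a harmless dose.** Sections 1.2.4.2 and 9.10.4 show that missing the criterion means enrolment continues toward 32, after which escalation proceeds absent a significant safety concern. The criterion is also permissive and sits beside a predictive probability, a Grade 3 thrombocytopenia clause and monthly unblinded review.
- **Adjustment makes the criterion stricter about real falls.** The overall false-pass rate at the margin is unchanged. At a true fall of 50,000, ANCOVA passes more often: 32%, 38% and 51% at correlations 0.3, 0.5 and 0.7, against 32% unadjusted. That is proper for a comparison against a 110,000 margin, but it is not added caution.

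It could also be said that the IDMC charter, which is not among the documents, may specify an adjusted analysis. Even so, the protocol states the criterion and its power, and a reader would take the comparison as unadjusted.

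**Conclusion.** The point holds as a conditional improvement. The criterion leaves out a baseline that every infant already has. Prespecified adjustment would change power from 78% to about 81–95% for correlations of 0.4 to 0.7, leave it level at about 0.3, and lose 3 to 4 points near zero. For any positive correlation it also removes the dependence of the result on which arm happened to start higher.

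These figures rest on normal counts, SD 75,000 in both arms, 8 per arm, no vaccine effect and an assumed correlation. A reader might infer that the stated 84% is an arithmetic error. It reproduces under a normal approximation (83.5%); what it does not match is a t interval (77.9%) or the Mann-Whitney test the protocol names (about 75.5%).

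All the power figures read the threshold as −110,000. Taken literally, the printed condition would almost never be met when the vaccine has no effect, adjusted or not. The printed condition and the sizing text must therefore be reconciled before any power figure describes the rule.

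**What to change.** In Protocol section 11.4:

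- Define the platelet comparison as the vaccine-minus-placebo difference from an ANCOVA of Day 31 count on arm and last pre-Dose-1 (Screening) count, with a two-sided 95% CI. Report the unadjusted difference alongside.
- State that the Day 30 count is not the baseline, because it follows Dose 1.
- Restate the power for that analysis, giving the assumed correlation and a range around it, and name one method for both the power and the interval.
- Reconcile the threshold printed in the escalation condition with the 110,000 decrease in the sizing paragraph.
- Carry the same definition into the instructions for the unblinded statistician who prepares the IDMC analyses.

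The cost is a few sentences and a small program change, with no extra infants or blood. The price is 3 to 4 points of power if the counts turn out nearly uncorrelated, plus the linearity and common-slope assumption.

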Dose escalation will proceed after administration of *two doses of* the vaccine to 32 subjects. *However*, in the absence of a *significant* safety concern detected in the regular monitoring of accumulating safety data *on at least 16 subjects, the IDMC may allow for dose escalation to proceed without the requirement of enrolling and evaluating the full group size of 32 subjects. A subsequent dose escalation will proceed after administration of two doses of the vaccine to between a maximum of 32 to a minimum of 16 subjects in the absence of a significant safety concern detected by the IDMC in the regular monitoring of accumulating safety data. Thus, upon review of the accumulating safety data on a minimum of 16 subjects after administration of two doses of the vaccine, the IDMC may decide that based on the evolving safety profile, sufficient information has been accumulated to allow safe progression to the next sequential dose level (Amended 10 December 2017)*. It will be ensured that, as a minimum the IDMC will have reviewed safety data of at least 16 subjects for two doses and given their formal approval prior to enrolling subjects to the next dose level.

Additionally, the IDMC will perform a review when all safety data up to 30 days after administration of Dose 2 in Step 3 (i.e. Day 60) are available.

Refer to Section 9.10.3 for more information about IDMC.

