11.8.2. Between groups assessment

Exploratory comparisons between the investigational RSV groups and the Placebo groups will be done in terms of the percentage of subjects, overall doses, reporting any Grade 2/3 AE during the 7-day follow-up period (Day 0-6) after vaccination, and/ or any fever >38.5°C during the 7-day follow-up period (Day 0-6) after vaccination, and/ or any vaccine-related SAE during the 7-day follow-up period (Day 0-6) after vaccination.

The standardized asymptotic 95% CI for the difference between the RSV groups and (minus) the Placebo groups will be computed.

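### Protocol Section 11.4 prints the platelet threshold for early dose escalation with the wrong sign: on vaccinee minus placebo, the lower 95% limit should exceed −110,000, not +110,000

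*Protocol*

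**What the plan says.** Amendment 4 lets the IDMC recommend moving to the next dose level on 16 infants rather than 32. Protocol Section 11.4 supplies a platelet criterion for that decision.

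- **Objective.** Unvaccinated counts are assumed to have mean 300,000/mm³ and SD 75,000, and the vaccinee mean should not fall below 190,000. The cohort of 16 (8 per group) is sized to "rule out a 110,000 platelets/mm³ decrease due to vaccination with 84% power", the power being calculated for a vaccine with no effect on platelets. The test is a one-sided 0.025 non-inferiority test.
- **Statistic.** After the first 16 infants have had both doses, "the 95% CI for the difference in mean platelets at Day 31 between vaccinees and placebo recipients will be calculated". The order of subtraction is not given.
- **Rule.** "If the lower boundary of the 95% CI is above 110,000" platelets/mm³, and the posterior predictive probability of no Grade 3 or higher thrombocytopenia in the next 16 infants is high enough (80% is given as an example), the IDMC may recommend opening the next dose cohort early.

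The Amendment 4 change log in Appendix D prints the same figure. The SAP does not state the criterion. Where the protocol does give an order of subtraction, for the exploratory adverse-event comparisons in Section 11.8.2, it is the vaccine groups minus placebo: "the difference between the RSV groups and (minus) the Placebo groups will be computed". SAP Section 6.4.1.2 uses the same order.

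**The concern.** The sizing paragraph and the decision rule do not describe the same test. Excluding a decrease of 110,000 means showing that the vaccinee-minus-placebo difference is greater than −110,000. The rule asks for a lower limit above +110,000, which would demonstrate a large increase.

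This is the only numeric frequentist criterion in either document for judging platelets on 16 infants instead of 32, in a first paediatric study where thrombocytopenia is the named prior concern. Applied literally, a harmless vaccine would almost never meet it, and the early look would lose its purpose. If it is not applied literally, whoever prepares the unblinded IDMC report must decide what was meant with the data in view.

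**Working it through.** **Inputs (Protocol Section 11.4).** n = 8 per group; SD = 75,000 in each arm; margin = 110,000; one-sided α = 0.025, equivalent to the lower limit of a two-sided 95% CI. Throughout, D = vaccinee mean − placebo mean, and L = lower 95% limit of D.

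**Standard error and half-width.**
- SE = 75,000 × √(2/8) = 37,500.
- t(0.975, 14 df) = 2.145, so the half-width is about 2.145 × 37,500 ≈ 80,400.

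**The plan's own figure.** Power to exclude a fall of 110,000 with no true effect, using L > −110,000:
- Normal approximation: Φ(110,000/37,500 − 1.96) = Φ(0.973) = 83.5%, against the stated 84%.
- t interval (noncentral t, 14 df, noncentrality 110,000/37,500 = 2.933): 77.9%.
- Exact Mann-Whitney, simulated: about 75%.

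The stated power is therefore recovered, by the normal approximation, with a bound of **−110,000**.

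**The rule as printed, L > +110,000.**
- Noncentrality with no effect is −110,000/37,500 = −2.933, so P(met) = 1.2 × 10⁻⁶, about 1 in 820,000.
- Observed difference needed: about 110,000 + 80,400 = 190,400 in favour of vaccinees.

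**Both rules side by side (D, t interval, SD 75,000).**

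| True effect on mean | Printed: L > +110,000 | Corrected: L > −110,000 |
|---|---|---|
| None | 0.0000012 | 0.779 |
| Fall of 50,000 | essentially 0 | 0.320 |
| Fall of 110,000 | essentially 0 | 0.025 |
| Rise of 110,000 | 0.025 | > 0.999 |
| Rise of 200,000 | 0.61 | essentially 1 |

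The corrected rule has its 2.5% error rate at a fall of 110,000, as the sizing paragraph intends. The printed rule has it at a rise of 110,000.

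**Sensitivity to SD (no true effect).** 75,000 and 47,500 appear in Section 11.4; 60,000 and 90,000 are my assumptions, to show a range.

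| SD | Printed | Corrected |
|---|---|---|
| 47,500 | 1.3 × 10⁻¹⁰ | 0.990 |
| 60,000 | 3.2 × 10⁻⁸ | 0.926 |
| 75,000 | 1.2 × 10⁻⁶ | 0.779 |
| 90,000 | 1.1 × 10⁻⁵ | 0.624 |

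**The opposite order, placebo minus vaccinee.** A lower limit above +110,000 is then evidence that vaccination lowers the mean by more than 110,000, the harm the test should exclude. Taken alone, the condition is met with probability 0.025, 0.17 and 0.61 at true falls of 110,000, 150,000 and 200,000. In this order a valid rule would use the **upper** limit, below +110,000.

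Adding the predictive-probability condition (prior mean 300,000 and SD 75,000, data SD fixed at 75,000, threshold 80%, 16 future infants), the joint probabilities at falls of 150,000 and 200,000 are about 0 and 0 if only vaccinee counts enter the posterior, or about 0.12 and 0.14 if both arms are pooled. Also requiring no vaccinee below 50,000 at Day 31 reduces the pooled figures to 0.05 and 0.02. The protocol does not say whose counts enter the posterior, so both variants are assumptions.

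**The case against.** The case against giving this much weight has substance.

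- **The sentence is not the operative escalation rule.** Section 1.2.4.2 provides, for a cohort of 16 or more with no significant safety concern, that "the IDMC may allow for dose escalation to proceed without the requirement of enrolling and evaluating the full group size of 32 subjects". Footnote d to Figure 1 and Section 9.10.4 say much the same, and none of them cites the threshold. Section 11.4 itself says only that the IDMC may recommend.
- **Other protections apply.** Holding rules 1d and 2c cover bleeding with low platelets and Grade 3 or higher laboratory abnormalities. The IDMC reviews unblinded data monthly. Section 11.4 has its own clause on Grade 3 thrombocytopenia in a vaccinee.
- **The natural literal reading fails safe.** An unmet criterion means enrolling towards 32, not escalating on harm.
- **The intention can be inferred** from the preceding paragraph, so literal application may be unlikely.
- **Section 11.8.2 concerns adverse-event percentages.** It does not define the order for mean platelets.
- **A minus sign might have been lost when the text was read from the PDF.**

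The first four points stand. They limit the consequence but do not make the sentence correct. The fifth is fair: Section 11.8.2 is supporting evidence for the order, and the conclusion does not depend on it because neither order rescues the text. The last cannot be fully excluded, and the change log is weak corroboration since it repeats the same amendment text. It is unlikely, because minus signs survive elsewhere, for example in the vaccine storage temperatures.

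**Conclusion.** The concern holds. The printed threshold contradicts the non-inferiority objective in the same section under either order of subtraction, and nothing in the protocol or SAP corrects it. On vaccinee minus placebo, −110,000 restores the intended behaviour: 78% to 83% with no effect, depending on the approximation, and 2.5% at the margin. The printed condition is met about once in 820,000, and no more than about once in 95,000 for SDs up to 90,000.

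These figures assume normal counts, equal SDs, 8 evaluable infants per arm and a pooled t interval. The direction of the error depends on none of these.

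The error does not by itself block escalation, and I do not claim it would expose infants to a harmful dose. It should be corrected because a pre-specified decision threshold for infant dose escalation is wrong as written and the intended value is clear.

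**What to change.** In Section 11.4, state both the order of subtraction and the bound: *the lower limit of the 95% CI for the difference in mean Day 31 platelets, vaccinee minus placebo, is above −110,000 platelets/mm³*. Placebo minus vaccinee with an upper limit below 110,000 is equivalent; use one form throughout.

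Make the same correction in any IDMC charter or analysis specification that copied the sentence; those documents were not available here.

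The cost is one sentence in an amendment or a clarification letter to the IDMC, with no change to data collection, sample size or analyses.
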